#### 5.3.1. Safety Population

All participants who received at least one dose of the vaccination and for whom any post-dose data is available will be included in the safety population.

### 5.3.2. Immunogenicity Population

The Immunogenicity Population will include all data from randomized who have received at least one vaccination and have the necessary data available to analyze a given endpoint.

### 5.3.3. Per-Protocol Population

The Per-Protocol population will include participants in the immunogenicity population with additional exclusions as needed for sensitivity analyses. The per-protocol population will specifically exclude:

- Study visits and/or vaccinations occurring out-of-window as defined by the study protocol
- Study visits where a major protocol deviation occurred
- Study visits occurring after a participant becomes ineligible after randomization

## 5.4. Covariates and Subgroups

Demographics will be summarized using descriptive statistics, and there are no specific covariates of interest or explicit sub-group analyses planned.

## 5.5. Missing and Outlier Data

All attempts will be made to collect all data per protocol. Frequencies of missingness for primary outcomes will be calculated overall and within each study group. Less than 10% missing data that are missing completely at random will be considered ignorable missingness and complete case analysis will be utilized. No imputation will be performed for missing values. Data visualizations such as boxplots, histograms, or scatter plots will be used to identify outliers. Single outliers may be identified if values are outside of 1.5x the interquartile range depending on normality assumptions. Outliers will not be excluded from the primary analyses. Outliers identified during the analysis will be discussed in the analysis report.

Measurements that occur outside of study visit windows may be considered missing in sensitivity analyses. Table S5 provides an overview of each study visit along with the visit window upper and lower bounds, as specified in the study protocol.

Table S6. Analysis Time Windows

Visit	Visit day (visit window in days)	Lower bound (days)	Upper bound (days)
Screen	-45 to -3	-45	-3
Visit 1 (V1)	1	1	1
Visit 2 (Safety & Immun)	15 ( $\pm 3$ )	12	18
Visit 3 (V2)	29 ( $\pm 7$ )	22	36
Visit 4 (Safety & Immun)	43 ( $\pm 3$ )	40	46
Visit 5 (V3)	57 ( $\pm 7$ )	50	64

Visit	Visit day (visit window in days)	Lower bound (days)	Upper bound (days)
Visit 6 (Safety & Immun)	58-59	58	59
Visit 7 (Safety & Immun)	64 ( $\pm 3$ )	61	67
Visit 8 (Safety & Immun)	71 ( $\pm 3$ )	68	74
Visit 9 (Safety & Immun)	169 ( $\pm 7$ )	162	176
Visit 10 /Exit 4 (Safety & Immun)	337 ( $\pm 7$ )	330	344
Phone Follow-up 1 (MAAE)	365 ( $\pm 7$ )	358	372
Phone Follow-up 2 (MAAE)	393 ( $\pm 7$ )	386	400

Measurements that occur outside of the scheduled protocol-specified assessment time-windows will be flagged and assigned to the intended study visit. These measurements will be included in the primary analyses; sensitivity analyses will be conducted to determine whether the results differ when these measurements, which occurred outside of the scheduled protocol-specified assessment time-windows, are excluded. Although multiple measurements occurring within the same assessment window are not anticipated to be an issue, if such an event occurs the analytic approach will be determined based on the specific measure and accounting for clinical rationale and standard approaches in the literature. For example, the minimum value, maximum value, earliest value or latest value may be considered for sensitivity analyses.

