6.3. Study Intervention Compliance

All IP is administered by the study team and documented on the Study Vaccine Administration CRF. A study vaccination outside of a participant's vaccination window may occur at the discretion of the PSRT.

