**DATE: 22 January 2024**

**SAP Revision History**

Revision Date	Analyst	Revisions/Justification
01Feb2023	[name]/[name]	Additional sensitivity analyses due to unanticipated vaccinations occurring out of study window
21 December 2023	[name]/[name]	Detailing interim Analysis plans for Humoral Immunity and dose response
11 January 2024	[name]/[name]	Finalized edits and Added CONSORT example diagram
18 January 2024	[name]/[name]	Clarified Interim analysis specifications for cellular response

Trial Initiation Date: first participant screened 08 Sept 2022

Trial Completion Date: last participant visit 29 Oct 2024

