#### **Analytical Approach for Cellular Immunogenicity Response**

The overall magnitude and quality of the antigen-specific T cell response will be assessed through detection of cytokine expression measured by flow cytometry. Measures at pre-vaccination and 2 weeks after each vaccination (weeks 2, 6, 10) will be assessed from all individuals divided by vaccination group. Levels of antigen-specific T cells will be compared between groups at both timepoints for Total responses (Boolean gating of flow cytometry data will be used to assess) and individual cytokines (IL-21, IL-2, TNF-a, IL-4, IFN- $\gamma$ , CD154). Polyfunctional scores and Heatmap of posterior probabilities via COMPASS analysis will be assessed using R software.

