## 8. IMMUNOGENICITY EVALUATION

### 8.1. Primary Immunogenicity Analyses

All summaries and analysis of immunogenicity data will be presented for the Immunogenicity Population. Humoral and cellular immunogenicity will be assessed primarily through descriptive statistics. Primary immunogenicity endpoints are IgG binding antibodies to g120 and antigen-specific CD4 and CD8 T cell responses.

The magnitude of plasma IgG (antigen-specific) responses will be measured by the endpoint titer at study weeks 0, 2, 4, 6, 8, 10, 24 and 48. Means or Geometric mean titers (GMTs) will be calculated for each group as appropriate based on the distribution, at each visit, and the per-participant peak response across all visits. Additionally, 95% confidence intervals (CI) will be computed using bootstrapping, or alternative methods. Results will be presented as exponentiated GMT and 95% CI. The distributions of GMTs will be compared across all vaccination groups via ANOVA (null hypothesis that the medians across all groups do not differ) at the 5%-statistical significance level, or using the Kruskal-Wallis test if ANOVA assumptions are violated; in the event Kruskal-Wallis testing is implemented the shape and scale uniformity across groups will be assessed for validity and results interpretation. Pairwise comparisons of GMT responses between dose groups at follow-up time points will be evaluated using a two-sided Mann-Whitney U test, with a Bonferroni-Holm step-down for adjusting p-values for multiple comparisons. Where necessary and appropriate, False Discovery Rates (FDR) will be calculated and reported using the Benjamini-Hochberg (BH) method.

The number and percentage of positive IgG responses to binding targets will be presented by vaccination group and visit based on input from the laboratory team. Differences between vaccinations groups will be evaluated using Fisher's exact test, or chi-squared tests.

Durability of IgG response will be assessed for each participant by estimating the decline in  $\log_{10}$  IgG from peak to 6 and 12 months (weeks 24 and 48 respectively) post final vaccination.

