## 8.3. Immunogenicity Sensitivity Analyses

Primary immunogenicity analyses conducted in the immunogenicity population may be repeated in the per-protocol population if per-protocol conditions are met. Results of primary analyses will be considered to be robust if effects are similar.

Examples of per-protocol sensitivity analyses include excluding study visits occurring out-of window, or where a major protocol deviation occurred. Bayes factors may be calculated and assessed for sensitivity analyses assessment.

If imbalance in participant demographic or clinical factors is detected between vaccination groups at the time of study enrolment, additional sensitivity analyses may adjust for imbalances in multivariable adjusted models.

Lastly, the presence of outliers will be evaluated using z-scores or boxplots for distributions, and if detected, sensitivity analyses may be performed excluding observations flagged as outliers.

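### Table S6 fixes the Visit 4 and Visit 8 windows to study day although doses 2 and 3 may move by 7 days, so the out-of-window sensitivity analysis tests calendar adherence, not time since dose

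*SAP*

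**What the plan says.** SAP 5.5 presents Table S6 as listing the "visit window upper and lower bounds, as specified in the study protocol". Protocol Table 1 has the same visit days and window widths. Neither document re-times a later visit when a dose moves.

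SAP 5.6.2 ties weeks 2, 6 and 10 (Visits 2, 4 and 8) to the doses: "Measures at pre-vaccination and 2 weeks after each vaccination (weeks 2, 6, 10) will be assessed". Weeks 6 and 10 are also two of the eight IgG time points in SAP 8.1, where magnitude is "measured by the endpoint titer at study weeks 0, 2, 4, 6, 8, 10, 24 and 48".

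The windows are used in two places.

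- SAP 5.5 keeps out-of-window measurements in the primary analyses, then commits to a check: "sensitivity analyses will be conducted to determine whether the results differ when these measurements" are left out.
- SAP 5.3.3 removes from the per-protocol population "Study visits and/or vaccinations occurring out-of-window as defined by the study protocol". SAP 8.3 makes the per-protocol repeat optional and adds: "Results of primary analyses will be considered to be robust if effects are similar".

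Doses did move. The SAP revision history records "Additional sensitivity analyses due to unanticipated vaccinations occurring out of study window". Protocol 6.3 also allows a dose beyond the "vaccination window may occur at the discretion of the PSRT".

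**The concern.** Visits 4 and 8 are placed 14 days after the nominal days of doses 2 and 3. If a dose moves and the sample window does not, the out-of-window flag no longer says how long after the dose the blood was drawn. A site that schedules from the actual dose can have well-timed samples flagged and removed. A site that follows the calendar can have mistimed samples kept.

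What is at stake is the value of the robustness check. SAP 8.3 reads similar effects as robustness. Agreement between the full analysis and one that removes samples on the wrong criterion says little about whether timing matters, and disagreement is equally hard to interpret. The per-participant peak and the AUC in SAP 8.1 draw on the same samples, so a wrong exclusion at week 6 or 10 can carry into them.

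**Working it through.** **Inputs** (SAP Table S6; same days and widths in Protocol Table 1). Each bound is reproduced as visit day ± window:

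| Visit | Day ± window | Bounds |
|---|---|---|
| Visit 3 (dose 2) | 29 ± 7 | 22-36 (15 days) |
| Visit 4 | 43 ± 3 | 40-46 (7 days) |
| Visit 5 (dose 3) | 57 ± 7 | 50-64 (15 days) |
| Visit 8 | 71 ± 3 | 68-74 (7 days) |

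The nominal spacing is 43 − 29 = 14 and 71 − 57 = 14 days.

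**Step 1: a sample exactly 14 days after the dose.** Let d be the dose day.

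- Visit 4: 40 ≤ d + 14 ≤ 46 requires d = 26 to 32. That is 7 of 15 permitted days in window and 8 out (Days 22-25 and 33-36).
- Visit 8: 68 ≤ d + 14 ≤ 74 requires d = 54 to 60. Again 7 in and 8 out (Days 50-53 and 61-64).

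**Step 2: how far after the dose an in-window sample can be.**

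- Visit 4: 40 − 36 = 4 days to 46 − 22 = 24 days.
- Visit 8: 68 − 64 = 4 days to 74 − 50 = 24 days.

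**Step 3: the same question with a tolerance.** Neither document states a post-dose tolerance for Visits 4 and 8. Visit 2 supplies one: its window is Days 12-18 and dose 1 is on Day 1, so it covers 12 − 1 = 11 to 18 − 1 = 17 days post-dose, that is 14±3.

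Let k be the number of days the dose is off nominal. Samples 11-17 days post-dose then fall on Days 40 + k to 46 + k (Visit 4) or 68 + k to 74 + k (Visit 8). The overlap with the fixed window is max(0, 7 − |k|) days:

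| Days off nominal | 0 | 1 | 2 | 3 | 4 | 5 | 6 | 7 |
|---|---|---|---|---|---|---|---|---|
| Sample days both in window and 11-17 days post-dose | 7 | 6 | 5 | 4 | 3 | 2 | 1 | 0 |

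So 13 of 15 permitted dose days leave at least one such sample day. Among permitted days, only Days 22 and 36 (dose 2) and Days 50 and 64 (dose 3) leave none. A dose further off than that also leaves none.

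**Step 4: an example at the edge.** Dose 2 on Day 36 is permitted. A sample on Day 50 is 14 days post-dose, and Table S6 flags it for exclusion. A sample on Day 40 is 4 days post-dose, and Table S6 keeps it.

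**Step 5: after re-anchoring.** With windows of dose + 14±3, a sample at exactly 14 days is within the timing limits for all 15 permitted dose days, so 0 of 15 are out against 8 of 15 now. One guard is needed. For dose 2 on Days 33-36, +17 falls on Days 50-53, when dose 3 is already permitted, so the Visit 4 sample must also precede dose 3.

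**The case against.** The best case for the plan is that calendar windows match its own time scale. SAP 8.1 defines the IgG analysis by study week and the AUC by visit week, SAP 4.7 lists humoral sampling by study day, and the interim humoral models use days since first injection. The two-weeks-after-vaccination wording sits in the cellular interim section. SAP 5.5 describes a check on protocol-scheduled timing, and a schedule-adherence check is legitimate. Out-of-window doses are already a separate per-protocol criterion.

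Much of this stands, and it limits the point. Three things remain. The schedule itself puts Visits 4 and 8 at 14 days after the nominal dose days, as it puts Visit 2 after dose 1. The vaccination criterion applies only in the optional per-protocol repeat. And it does nothing for a dose 4 to 7 days off nominal, which is in window although its exact 14-day sample is not.

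A reader might infer more than the documents support:

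- *More than half of samples are misclassified.* The 8 of 15 counts permitted days at zero tolerance. The documents give no distribution of dose dates, and do not say how many doses were out of window or in which direction.
- *No sample can satisfy both criteria.* That holds only for a dose 7 or more days off nominal.
- *Every post-dose visit needs a new window.* Visits 6 and 7 are not among the SAP 8.1 IgG time points (SAP 4.7 goes from Day 57 to Day 70). At Visits 9 and 10 the nominal offsets (169 − 57 = 112 and 337 − 57 = 280 days) stay in window for all 15 permitted dose-3 days. SAP 4.7 and 8.1 also speak of 6 and 12 months after the final vaccination, so the documents do not settle a post-dose offset for those two visits.

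**Conclusion.** The point holds as a limited flaw in a sensitivity analysis. For Visits 4 and 8 the Table S6 flag measures adherence to the calendar, and once a dose moves it can disagree with time since dose: 8 of 15 permitted dose days at exactly 14 days, and 2 of 15 with no overlap at all under a ±3 day tolerance. It affects the committed SAP 5.5 exclusion analysis and, if it is run, the per-protocol repeat.

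It would be wrong to conclude that the trial's main results are biased. The primary endpoints are safety, the primary immunogenicity analyses keep all samples, and no estimate or test is shown to change.

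The finding assumes that Table S6 is applied as written. The arithmetic is exact. The 14±3 day tolerance is borrowed from Visit 2. The number of samples affected cannot be derived from the documents. The protocol does not state from which date its visit windows run, so site practice may differ from Table S6.

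**What to change.** Amend SAP 5.5 as follows.

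1. Keep the Table S6 protocol windows for deviation reporting and for the per-protocol definition in SAP 5.3.3.
2. For the SAP 5.5 exclusion analysis, add analysis windows counted from the actual preceding vaccination date: Visit 4 = dose 2 + 14±3 days and before dose 3; Visit 8 = dose 3 + 14±3 days. Leave the other visits as they are.
3. Flag samples that follow an out-of-window vaccination separately, and report the analysis with and without them.
4. State that a visit can be a schedule deviation and still be in window for analysis.
5. Correct the SAP 5.5 pointer from Table S5, which is the power table, to Table S6.

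The cost is a short SAP edit, for which SAP 11 leaves room by providing for an update before unblinding. Vaccination dates (Listing 1) and sample collection dates (SAP 5.6.1) are already planned for use, so no new data and no protocol amendment are needed, and no dosing or visit rule changes. The report will need a note explaining visits that are schedule deviations but in window for analysis.

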B-Cell Analysis		17	17	17	17	17	17		17	17	17	17	
Multiparameter Flow Cytometry		17	17	17	17	17	17		17	17	17	17	
Innate Cell Analysis		17	17			17			17	17	17	17	
Transcriptomics		2.5	2.5	2.5	2.5	2.5	2.5		2.5	2.5	2.5	2.5	
Additional Immunogenicity Testing		42.5	8.5	8.5	8.5	8.5	8.5		17	25.5	34	34	

Visit Number	0	1	2	3	4	5	6	7	8	9	10 ² /Exit 4	Phone Follow-up #1	Phone Follow-up #2
Visit Type	Screen	V1	Safety & Immun	V2	Safety & Immun	V3	Safety & Immun	Safety & Immun	Safety & Immun	Safety & Immun	MAAE follow-up	MAAE follow-up	MAAE follow-up
Visit Day	-45 to -3	1	15	29	43	57	58-59	64	71	169	337	365	393
Window			± 3d	± 7d	± 3d	± 7d		± 3d	± 3d	± 7d	± 7d	± 7d	± 7d
Visit Week	0	2	4	6	8	8	9	10	24	48	52	56	
Daily Volume (mL) ⁶	23	111.5	85	60.5	85	60.5	19.5	70.5	102	100	108		
Cumulative Volume (mL)	23	134.5	219.5	280	365	425.5	445	515.5	617.5	717.5	825.5		
8-Week Cumulative Volume (mL)						402.5	422	381	483	100	108		

SP = Assay performed from stored plasma; no additional blood volume required

¹ Full physical examination at screening (visit S1) and targeted physical examination at all other visits; Vitals to be collected both pre- and at about 30 minutes post-vaccination at Visit Day 1, 29, and 57.

² Participants will be contacted for the unblinding visit after the clinical data is locked.

³This includes unsolicited AEs which will be collected until 28 days post each vaccination.

⁴Medically Attended AEs will be followed through the end of the study, a full 12 months following the last vaccination. After clinic visits end, follow-up for MAAEs will occur by monthly phone calls for two months.

For those participants who are unable to continue participation in the study, but who do not withdraw consent, an exit visit will be conducted.

⁵ Research labs may be performed at any visit where sufficient stored samples are available

⁶ Blood volumes for clinical lab assays may be adjusted as long as maximum daily blood volume is not exceeded.

⁷ Pregnancy tests can be conducted at any visit if clinically indicated.

⁸ Any clinically indicated safety labs can be obtained at investigator discretion

^{*}10 mL EDTA verification blood collection for HIV incident case resolution for enrolled participants.

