7.2.1. PSRT

The PSRT will include the following:

- Sponsor's Medical Expert or designee
- HIV Vaccine Product Manager or designee
- ORA Pharmacovigilance (PVG) Physician
- PI or designee
- Independent Safety Monitor (ISM)

Additional PSRT participants may include, as needed, the following:

- Associate Investigators
- Clinical research nursing staff
- Laboratory directors

- Data management and regulatory staff
- DAIDS Medical Officer

PSRT conference calls or meetings will require, at minimum, the participation of the Sponsor's Medical Expert or designee, ISM, and the PI or designee. The WRAIR IRB will be notified of the decisions taken by the PSRT if they involve suspensions, clinical holds (voluntary or involuntary), or terminations of this research in accordance with [Table 8](#). The USAMRDC ORA PSSO will be responsible for safety reporting to the U.S. FDA.

The DAIDS Medical Officer will serve in a consultant role on the PSRT but is not required for PSRT or any other protocol team decisions.

Participants who are discontinued from additional study vaccinations will be discussed with the PSRT to determine the duration, if any, of follow-up visits to further evaluate safety and monitor adverse experiences.

Wherever possible, the tests and evaluations listed for the termination visit should be carried out if the subject refuses follow-up according to the protocol visit schedule.

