7.3. Participant Discontinuation/Withdraw from the Study

A participant may withdraw from the study at any time at his/her own request, or may be withdrawn at any time at the discretion of the investigator for safety, behavioral, or administrative reasons. Reasons may include the following:

- Repeated failure to comply with protocol requirements
- Recommended withdrawal by the study investigator, e.g., because of worsening health status, intercurrent illness, or AEs interfering with study assessments as determined by the investigator
- Participant requests withdrawal.

If the participant withdraws consent for disclosure of future information, the sponsor's representative may retain and continue to use any data collected before such a withdrawal of consent. If a participant withdraws from the study, he/she may request destruction of any samples taken and not tested, and the investigator must document this in the site study records. Participants who acquire HIV will be discontinued from study vaccinations, and additional research blood draws will not be performed. However, the participant will continue with safety assessments: pregnancy test, CBC with differential, and Creatinine/ALT.

Refer to the schedule of activities in [Table 1](#) for data to be collected at the time of study discontinuation and follow-up and for any further evaluations that need to be completed.

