Total immune responses over time will be assessed by the positive incremental area under the curve (AUC). An AUC curve will be constructed with raw, unlogged endpoint titers on the y-axis and visit week on the x-axis (week 0 to week 48). AUC will be logged after calculation from raw values. For comparability between participants with different numbers of samples (visits) available, these values will be scaled (normalized) by the week of the last available sample. If no sample is available for visits other than the first and last, no explicit imputation will be done, and the AUC will be calculated based on available samples. Log AUC will be analysed similarly to the visit-by-visit titers and presented as mean AUC and 95% CI.

The magnitude of CD4+ and CD8+ T-cell effector function and polyfunctionality will be evaluated through response by cytokines such as IFN- $\gamma$  and IL2. The frequencies of CD4 or CD8 T cells responding to each test antigen with IFN- $\gamma$  and/or IL2 will be calculated using the following categories: all IFNy+, all IL2+, IFNy and IL2+, IFNy or IL2+. Descriptive statistics will evaluate the distribution of CD4+ and CD8+ responses and polyfunctionality scores by vaccination group and visit. Differences in CD4+ and CD8+ responses between vaccination groups at each visit will be evaluated using Kruskal-Wallis tests, and pair-wise comparisons of

particular visits will be performed with two-sided Mann-Whitney U test, with a Bonferroni-Holm step-down for adjusting p-values for multiple comparisons.

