## APPENDIX 1: ADDITIONAL TABLES AND FIGURES

**Table 1: Participant Disposition by Vaccination Group**

Participant Disposition	200 µg ALFQ (N=X)		100 µg ALFQ (N=X)		50 µg ALFQ (N=X)		All Participants (N=X)	
	n	%	n	%	n	%	n	%
Screened	--	--	--	--	--	--	--	--
Enrolled/Randomized	x	100	x	100	x	100	x	100
Received Study Vaccination Dose 1 (Visit 1, Day 1)	x	xx	x	xx	x	xx	x	xx
Completed Visit 2 (Day 15)	x	xx	x	xx	x	xx	x	xx
Received Study Vaccination Dose 2 (Visit 3, Day 29)	x	xx	x	xx	x	xx	x	xx
Completed Visit 4 (Day 43)	x	xx	x	xx	x	xx	x	xx
Received Study Vaccination Dose 3 (Visit 5, Day 57)	x	xx	x	xx	x	xx	x	xx
Completed Visit 6 (Day 58-9)	x	xx	x	xx	x	xx	x	xx
Completed Visit 7 (Day 64)	x	xx	x	xx	x	xx	x	xx
Completed Visit 8 (Day 71)	x	xx	x	xx	x	xx	x	xx
Completed Visit 9 (Day 169)	x	xx	x	xx	x	xx	x	xx
Completed Visit 10/Exit (Day 337)	x	xx	x	xx	x	xx	x	xx
Phone Follow-up #1 (Day 365)	x	xx	x	xx	x	xx	x	xx
Phone Follow-up #2 (Day 393)	x	xx	x	xx	x	xx	x	xx
Note: N = Number of randomized participants								

Table 2: Summary of Demographic and Baseline Characteristics by Vaccination Group

Variable	Characteristic	200 µg ALFQ (N=X)		100 µg ALFQ (N=X)		50 µg ALFQ (N=X)		All Participants (N=X)		p-value
		n	%	n	%	n	%	n	%	
Age	18-29	x	xx	x	xx	x	xx	x	xx	
	30-39									
	40-49									
	50+									
Age, years	Mean									
	Standard Deviation									
	Median									
	Q1 (25 th percentile)									
	Q2 (75 th Percentile)									
Gender	Male									
	Female									
	Transgender									
Sex at birth	Male									
	Female									
	Undifferentiated									
Level of Education										
	Primary education									
	Secondary education									
	Undergraduate degree									
	Graduate									
	Other									
Race	White									
	Black or African American									
	Asian									
	American Indian/Alaskan Native									
	Native Hawaiian or Other Pacific Islander									
	Multiracial									
	Other									
Ethnicity	Non-Hispanic/Latino									

Variable	Characteristic	200 µg ALFQ (N=X)		100 µg ALFQ (N=X)		50 µg ALFQ (N=X)		All Participants (N=X)		p-value
		n	%	n	%	n	%	n	%	
	Hispanic/Latino									

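### Early-exit samples have no analysis visit except Visit 10 (Day 337), so they can enter the primary week-48 titer, decline and AUC as if drawn at week 48

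*SAP*

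**What the plan says.** - **An exit visit exists.** Protocol 1.3, Table 1 notes: "For those participants who are unable to continue participation in the study, but who do not withdraw consent, an exit visit will be conducted". The SAP schedule repeats the note.
- **Its bloods.** Protocol 7.3 refers to Table 1 "for data to be collected at the time of study discontinuation and follow-up". The Visit 10/Exit column there is a safety-and-immunogenicity visit with research draws. For people taken off vaccination, Protocol 7.2.1 adds that, where possible, "the tests and evaluations listed for the termination visit should be carried out if the subject refuses follow-up".
- **Its row.** SAP Table S6 has a single line, "Visit 10 /Exit 4 (Safety & Immun)", for Day 337 with bounds 330 to 344. The disposition shell (SAP Appendix 1, Table 1) likewise has one line, "Completed Visit 10/Exit (Day 337)".
- **The out-of-window rule.** SAP 5.5: "Measurements that occur outside of the scheduled protocol-specified assessment time-windows will be flagged and assigned to the intended study visit". Then: "These measurements will be included in the primary analyses". A sensitivity analysis without these values is committed.
- **The analyses.** SAP 8.1 compares titers at nominal weeks up to 48, takes the decline from peak to weeks 24 and 48, and draws the AUC with "visit week on the x-axis (week 0 to week 48)", scaled by the week of the last available sample. Only the interim AUC (SAP 5.6.1) measures time by collection date.

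**The concern.** A person who leaves at, say, week 12 and gives an exit sample has a value whose only listed analysis visit is Visit 10. It lies far outside Days 330-344, so the out-of-window rule applies, and the only visit it can be matched to by name is week 48. A week-12 titer would then count as persistence at week 48. In the AUC, the line from the last scheduled sample would be drawn straight across to week 48.

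Magnitude, durability and AUC are the named elements of the secondary IgG endpoint, and immunogenicity is one of the comparisons meant to determine the optimal ALFQ dose. With about 20 people per arm, a few misplaced values can matter. The disposition line would also count an early exit together with people who completed Day 337.

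**Working it through.** **1. The plan's own figure, for scale.** Three-arm one-way ANOVA, n = 20 per arm, SD 0.2, extreme means 0.202 apart with the third midway: λ = n × 2 × (d/2)² / SD² = 20 × 2 × 0.101² / 0.04 = 10.2. With 2 and 57 degrees of freedom, power is 0.8017 against 0.802 stated. This is not in dispute. It was calculated for peak titer, not week 48.

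**2. Assumed inputs.** The documents give no titer curve and no dropout rate. Assume log10 titers of 2, 3, 3, 4.3, 4.1, 5, 4.3 and 3.7 at weeks 0, 2, 4, 6, 8, 10, 24 and 48, and 4.9 at a week-12 exit.

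**3. Normalised AUC for one person** (SAP 8.1: raw titers minus baseline, trapezoids, divided by last sample week).
- Area to week 10: 900 + 1,800 + 20,753 + 32,342 + 112,389 = 168,184.
- Completer: 168,184 + 838,268 + 297,174 = 1,303,626; divided by 48 = 27,159.
- Week-12 exit labelled week 48: the last segment is (99,900 + 79,333)/2 × 38 = 3,405,423. Total 3,573,607; divided by 48 = 74,450. Ratio to completer 2.74.
- Same sample at its true week: the last segment is 89,616 × 2 = 179,233. Total 347,417; divided by 12 = 28,951. Ratio 1.07.
- Exits at weeks 14 and 18 (assumed 4.8 and 4.6): ratios 2.50 and 2.16 if labelled week 48, and 1.30 and 1.49 at the true week.

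**4. Direction by time of exit** (exit value labelled week 48, same curve; a completer's decline is 5.0 − 3.7 = 1.3).

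| Exit | Exit titer | Change in 20-person week-48 mean, per exit | AUC ratio to completer | Recorded decline from own peak |
|---|---|---|---|---|
| Week 12, after dose 3 | 4.9 | (4.9 − 3.7)/20 = +0.06 | 2.74 | 0.1 |
| After dose 2 (samples to week 6) | 4.1 to 4.3 | +0.02 to +0.03 | 0.54 to 0.66 | 0 to 0.2 |
| After dose 1 (samples to week 2) | 3.0 | (3.0 − 3.7)/20 = −0.035 | 0.03 | 0 |

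**5. Arm level, k post-dose-3 exits among 20.**
- Week-48 mean: k/20 × 1.2 = 0.06, 0.12, 0.18 log10 for k = 1, 2, 3 (GMT × 1.15, 1.32, 1.51). The mean decline shrinks by the same amounts.
- Mean log10 AUC: k/20 × log10(2.74) = k/20 × 0.438 = 0.022, 0.044, 0.066.
- With other gaps D between the exit titer and week 48, the week-48 shift is kD/20. For k = 1 to 3 it is 0.025 to 0.075 at D = 0.5, 0.05 to 0.15 at D = 1.0, and 0.075 to 0.225 at D = 1.5.

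**6. Spread and tests** (simulation borrowing SD 0.2 and effect 0.202 from the peak-titer design; D = 1.0). One misfiled value in 20 raises the within-arm SD from 0.20 to about 0.30. With one in every arm, ANOVA power falls to about 0.34, against about 0.78 if those samples stay out of week 48. With no true difference and misfiled values in one arm only, ANOVA rejects in about 5%, 10% and 24% of runs for k = 1, 2 and 3.

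**The case against.** The strongest reply is that the SAP does not order this. It leaves the intended visit undefined, and a programmer could well decide that a week-12 exit draw was never meant as Day 337. The out-of-window additions to the SAP were prompted by mistimed vaccinations. Scaling the AUC by the last sample week suggests that some people were expected to finish before week 48. This stands in part: misfiling is a path the plan leaves open, not an instruction. But no text closes it, and scaling does not help if the last week is recorded as 48.

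A reader might infer that the bias is always upward and favours the most reactogenic arm. The documents do not support that. The rules in Protocol 7.2 stop further vaccination, so they act before the series is complete, where AUC falls. Stopping vaccination is also not leaving the study: Protocol 7.2.1 leaves follow-up to the safety review team.

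Other points that stand:
- The 2.74 ratio belongs to one person; the SAP compares log AUC by arm, where the shift is small.
- Pairwise titer tests are Mann-Whitney with Holm adjustment. In a null simulation with D = 1.2 and 2 or 3 misfiled values in one arm, they rejected at least once in about 4-7% of runs. Kruskal-Wallis replaces ANOVA if its assumptions fail.
- Values are flagged, the exclusion analysis is committed, outliers are to be discussed, and a per-protocol repeat is possible.
- Not every leaver gives an exit research sample: those withdrawing consent are asked only for clinical assessments, and those who acquire HIV have no further research draws.
- Retention is also visible in the flow diagram, Listing 2 and the phone-contact rows, so only one disposition line is affected.

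**Conclusion.** The point holds as a gap in the mapping rule. Early exit and Visit 10 share one row, out-of-window values join the primary analyses at any distance, and the final AUC runs on nominal week, so an early-exit sample can be analysed as week 48. The sign of the error varies with time of exit. For 1 to 3 post-dose-3 exits among 20 and an assumed 1.2 log10 gap, the week-48 mean moves 0.06 to 0.18 log10 and mean log10 AUC about 0.02 to 0.07. All sizes rest on assumed waning and exit counts.

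It would go too far to say that the trial's results will be inflated, or to read 0.202 as the threshold for week 48, since that figure was set for the peak. A peak already recorded at week 10 is unchanged by a later, lower value. The sensitivity analysis could reveal the problem, but it removes every out-of-window value together and leaves the primary result as it is. Should-fix.

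**What to change.** - In SAP Table S6 and SAP Table 1 (disposition), separate Visit 10 (Days 330-344) from early exit, and count early exits apart from Visit 10 completers.
- Map an exit sample to the scheduled window in which its collection day falls. Otherwise treat it as unscheduled and keep it out of the week-48 GMT and decline.
- In the final AUC, use actual collection day for both the time axis and the last-sample scaling, as SAP 5.6.1 does at interim.

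The cost is SAP wording, one extra row in two tables and a mapping step in the programs; SAP Section 11 already provides for an update before unblinding. There would be slightly fewer week-48 values. On the plan's ANOVA assumptions, losing one per arm gives power of about 0.78, and two per arm about 0.75 to 0.76. One limit remains: an early leaver's normalised AUC still covers a shorter period than a completer's (ratios 1.07 to 1.49 above), so early leavers should be identifiable in the AUC results.
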